2.6 Deviations from the original plan and proposed mitigation actions

Already since the beginning of the study, due to delays in obtaining the Ethical Committees' approval in Nancy (France) and to limited availability of the FrailSafe system devices, there was a certain delay that affected the starting of mainly group A and partially of group B.

We have elaborated a proposed mitigation plan of a modified timetable for FrailSafe home visits in order to catch up with "lost" FS evaluations in group A, schematically depicted as following:

M 11	M		M 14	M 15	M 16	M 17	M 18	M 19	M 20	M 21	M 22	M 23	M 24	M 25	M 26	M 27	M 28	M 29	M 30	M 31	M 32	M 33	M 34	M 35	M 36
A1 a		B1	A1 b		32	A1 c		3	_	4		5		36		57		A2					up C		
Le	ege	nd:																							
А	1a			M1	.1						firs	t cyc	le fir	rst pa	rt 1-	-27(c	one r	nont	th)						
A	1b			M1	.4						firs	t cyc	le se	econc	l par	t 28-	·52(c	one r	nont	th)					
A	1c			M1	.7						firs	t cyc	le th	ird p	art 5	53-80)(one	e mo	onth)						
A	2			M2	8-30)					sec	ond	cycle	e 1-8	0 (th	ree I	mon	ths)							
В	1			M1	2-13	3					firs	t cyc	le 81	1-120)										
В	2			M1	.5-16	5					sec	ond	cycle	e 81-	120										
В	3			M1	8-19)					thir	d cy	cle 8	31-12	0										
B	4			M2	20-21	L					fort	h cy	cle 8	31-12	0										
В	5			M2	2-23	3					fiftl	п сус	le 8	1-120)										
В	6			M2	4-25	5						•		1-12											
В	7			M2	26-27	,					sev	enth	сус	le 81	-120	1									

Figure 2. Mitigation action proposed for the FrailSafe system sessions

More analytically the plan proposes:

- The split in three of group A's first cycle of FrailSafe session and its interference between the 1st-3rd sessions of group B (M11,M14, M17)
- The decrease of the duration of FS session for group A (3-5 days instead of 5)*
- The reduction for group B of the total number of FrailSafe sessions' cycles in 7 (instead of 9 initially scheduled)
- No change in the conduction of the study for groups C and D (M31 and after).

*this proposal about the duration derives from the need to do all 80 first FrailSafe sessions per center in the shortest delay possible in order not to disturb too much the continuation of the study with the recruitment of group B. Taking into account that no more than five FrailSafe sessions can run simultaneously because of material and personnel availability reasons, the shortest time frame possible to make 80 FrailSafe home sessions is almost 3 months, as illustrated in the following schema:

H2020-PHC-690140-FRAILSAFE

D2.1r: Clinical Study Methodology Revised

	Week 1	Week 2	onth A1 Week 3	Week 4	Week 5	Week 6	onth A2 Week 7	Week 8	Week 1	Week 2	onth A3 Week 3	Wee
	Week 1	S MT WT E S	C MT WT E C C	Week 4	Week 5		S MT WT E S	S MT WT F S S	Week 1		Week 3	S MT WT
	x x	3 1011 001 F 3	3 1011 001 F 3 3			3 3 WI VI F 3	3 111 11 11 1 5	3 WI WI F 3 3	IVI I VI F 3 3		3 1011 001 F 3	3 101 1 00 1
	xx											
	x x											
4	x x x x											
5												
6	x x x	x										
7	x x x	x										
8	x x x	x										
9		x x x										
10		x x x										
11		x x x x										
12		x x x x										
13		x x x x										
14 15			x									
16		x x ×	x									
17			x x x x x x									
18			x x x									
19												
20			x x x x x x x x									
21												
22			x x x x x x x x x x x x x x x x x x x	x								
23			x x x x	x								
24				x x x								
25				x x x								
26				x x x x								
27				x x x x								
28				x x x x								
29				x x x x	×							
30 31				x x x	×				┠┼┼┼┼┣		▋┼┼┼┦	
					× x x							
32					x x x							
53					x x x							
33 34 35 36					x x x x							
26					x x x x							
37					x x x x							
38					x x	c x x						
39						x x x						
40						x x x						
11						x x x x						
12						x x x x						
43												
44						x x x x	x					
15						x x x	x x					
46							x x x					
47							x x x					
48							x x x					
49							x x x x	×				
50 51							x x x x	×				
51							x x x	x x				
52							× × ×	x x x x	┠┼┼┼┼┻		▆┼┼┼┦	
53 54 55 56 57							x x ×	××××				
55								x x x x x x x x x x x				
56								x x x x				
57								x x x x				
8								x x x x	x			
9									x x x			
50									x x x			
50 51									x x x			
52									x x x x			
i 3									x x x x x x x			
54									x x x x	×		
55									x x x x	×		
56									x x x x			
67										x x x		
58	++++									x x x x x		
59	+									x x x x		
70										x x x x x x x x x x x x x x x x x x x x x x x x		
/1	++++								┠┼┼┼┼┣	x x x x	▆▎┼┼┼┼┦	
²	+ $+$ $+$ $+$								┠┼┼┼┼┣	x x x	x x	
73	++++								┠┼┼┼┼┣	x x x	x x	
/4	+ $+$ $+$ $+$								┠┼┼┼┼┣		x x x	
15											x x x	
75											× × ×	
70 71 72 73 74 75 76 77 78 78 79 80									┠┼┼┼┼┣			
ŏ	+ $+$ $+$								┠┼┼┼┼┣			
-												x
0												

x visit for installation of FS material

x "on call"=possible visit if problem

x visit of retrieval of FS material

weekend

Figure 3. Schema illustrating the whole group A's first FrailSafe session in terms of time (80 subjects per center in less than 3 months' time)

We propose the splitting of group A's FrailSafe sessions and their distribution in between the sessions of group B.

The alternative of having all 80 group A's FrailSafe sessions in 3 consecutive months is not considered preferable because it will delay the FrailSafe sessions of group B's by the same amount of time (3 months), resulting in further protocol deviations for group B also.

We wish to preserve the integrity of the initial protocol for group B in terms of:

-the synchronization of the first FrailSafe system sessions with the corresponding clinical evaluations

-and the duration of the FrailSafe sessions, which will remain 5 days as originally predicted.

The time required for accomplishing each FrailSafe session cycle in 40 participants per center is 2 months as depicted in the following schema:

													nor	ith	вт			-												• •								non	th B				_						-	
	_			ek 1	_						ek 2	-					eek	_				w							Vee		-					ek (_				We		_					eek	_	
OUP B		_	_	_	S	S	м	т	w	/ T	F	S	S	м	т	w	т	F	s s	м	т	w	т	F	S 5	5 1	мт	w	т	F	S	S	м	T۱	w	r f	S	S	м	т	w	TF	S	S	м	T	w	т	F	S :
		x x			-							-		⊢				_													-						-						_		Ŀ					
		xx			-		H					-		⊢				_													-						-						-		⊢					
83			x		-			x				-		H				-													-						-						-		F				_	
84		×	x	-	-			x				-		⊢				-													-			-									-		⊢					
85 86			x	x	-		×	x				-		⊢				-													-						-						-		F				_	
87					-		Ĉ				x	-		F				-																									-							
88			+				Ê				x			×				-																									-							
89							E				x				x																														E				-	
90			+								x					x																																	_	
91																	x	x																															_	
92														×	x	x	x	x																															_	
93																x	x	x		x	x																												_	
94																x	x	x		×	x																													
95																	x	x		×	x	x																												
96																				×	x	x	x	x																										
97																		_		×	x	x	x	x																										
98																		_				x	x	x		þ	x x																_							
99																		_				x	x	x		P	x x										_						_							
100					_							_						_					x	x		2	x x	×			-						-						_							
101	_				-							-		L				_								P		x			-						-						_							
102		_		-	-							-		⊢				_								2	××	x			-			_			-						_		⊢					
103					-							-		⊢				_													-		x				-1						-		⊢					
104					-		Ŀ					-		⊢				_										×	x		-			x			-						-		Ŀ					
105 106					-							-		⊢				-											X	x				x			-						-		⊢					
100					-		H					-		F				-													-					c x	_						-		F				_	
107		-		-	-		E					-		F				-															×			c x	_		x				-		F	-			-	
100												-		⊢				-																		(x	_			x			-		F				_	
110														F																				_		< x	_				x								_	
111														F																											x y	×							_	
112														F																											x >								_	
113														F																											×				×	x			_	
114																																									×					x				
115)	× ×			x	x	x			
116																																															x	x	x	
117																																													x	x	x	x	x	
118																																															x	x	x	
119																																															x	x	x	
120																																																x	×	

Legend:

х

х

visit for installation of FS material

"on call"=possible visit if problem

visit of retrieval of FS material

weekend

End of a cycle

Figure 4. Schema illustrating the first cycle of group B's first FrailSafe session in terms of time (40 subjects per center in 2 months' time). The same pattern should be repeated another 6 times completing the 7 FrailSafe sessions proposed by the mitigation plan.

By the time this revised version is written (beginning of M23), there has been a delay of approximately 3 months' time for group B FrailSafe sessions. The consortium's intention is to

. .

respect the protocol at its mitigated version so that the data analysis is the most robust possible. We consider the aforementioned plan as a competent one, since it has been effective in catching up with at least part of the initial delay (e.g.,. Nancy's clinical centre managed to synchronize its actions with the other centres), whereas its current delay is mostly the result of occasional difficulties and particular circumstances (e.g., reduced availability of several participants during summer time, extra time required for replacing individuals that dropped off, etc). Therefore, and despite the current delay, we consider that this schedule should continue to be followed by clinical centres.

However, the re-evaluation of the status of the clinical study, the alternatives offered at the time and the possibility of a request for a study prolongation will be reconsidered in M27, which is the month that the FrailSafe home sessions are supposed to be completed. Based on the number of sessions achieved by that time, and mostly on the results of the data analysis that will be performed, a more concrete and informed decision about the need and the required duration of a prolongation period will be taken by the consortium and proposed to the Commission. We consider M27 more appropriate than the present moment, since MO3 (=use quantitative and qualitative measures to predict short and long-term outcomes) will be better served in an analysis performed later on and thus a more precise estimation of the prolongation needed can be done at the time. Potential changes detected later on in the timeline of the project also serve better MO5 (provide a model sensitive to change...) and thus the postpone of a mitigation decision will work in favour of the right decision to take, because of the availability of more data. Acceptability issues, mainly addressed by MO7 (achieve all with a safe and acceptable to older people system) should be a consideration before immediately rushing to the prolongation option, that could induce a type of inconvenience in older people's routine.

3. Parameters, measurements and tools

3.1 Clinical evaluation-Comprehensive Geriatric Assessment

The clinical evaluation session employs the classical means that are routinely used in clinical practice up until now in order to detect and quantify frailty, globally evaluate the older patient's health and organise strategies of management. The comprehensive geriatric assessment is a laborious and generally time consuming complex procedure, initially analytic and eventually synthetic, which requires skills and expertise. To facilitate, speed up and broaden the applicability of CGA, many tools have be developed and proposed for each of its aspects, mostly in the form of detection or evaluation short scales.

For our clinical assessment sessions we have chosen widely recognized and used scales and questionnaires and also some structured questions that correspond to the needs for data collection of this study. Moreover, we employ some metrics of anthropometric and cardiovascular parameters (height, weight, body mass index, body fat, arterial blood pressure, pulse wave velocity and central systolic pressure), using adapted instruments. The battery of questions and the clinical measurements that are used will remain mostly the same all throughout the study's duration, with the exception of some data that are going to be collected only once in the beginning and potential need for additional information collection if this is required during the study's development and adaptation process.

The clinical evaluation session will be divided in assessment subsets, corresponding at different aspects of CGA (table 3).

Table 3. Clinical assessment's subsets	Tools to be employed
1. Identification data	Questions
 Generalities: demographics, leisure, social life/communication assessment 	Questions
 Medical history, comorbidities, medication list 	Questions, self-reporting, drug prescriptions, medical records when available
 Clinical examination and instrumental measurements 	Pulse palpation, measure tape, FORA scale, electronic tension meter, mobilograph
5. Balance and gait evaluation	Stopwatch, meter, IMUs
 Fried's criteria of frailty assessment: allocation into frailty categories 	Questions, dynamometer
7. Sensory system evaluation: vision, hearing	Questions and clinician's estimation
8. Nutritional Assessment	MNA short and extended form
9. Activities of Daily Living	Katz Index of Independence of ADL, Lawton IADL scale
10. Cognitive, mood and sleep evaluation	MMSE, MoCA, questions, GDS- 15items
11. Self-evaluation scales	Questions and VAS

The very first clinical evaluation session is divided in two parts. In the first part identification data is recorded (assessment subset 1,2-table 4,5), the Fried's criteria of frailty are examined

(assessment subset 6-table 9), the comorbidities are recorded (assessment subset 3-table 6), a short cognitive assessment takes place (assessment subset 10-table 13). This very first evaluation allows the verification of inclusion and exclusion criteria (table 1) and the classification to frailty levels and comorbidities' status. If a seemingly eligible in the beginning subject turns out, by this first part of the clinical evaluation, to have for example a MMSE<24, an active psychiatric disorder, an alcohol or drug abuse, or a poor prognosis condition, this subject will exit the study and will be replaced by another one. In other case, after the confirmation of the subject's eligibility to the study, the randomization and the allocation to groups, the rest of the clinical evaluation takes place (assessment subset 4, 5, 7, 8, 9, 11).

After this first clinical evaluation session, the rest that follows will take place as a single battery at the same time.

Together with the clinical assessment subsets, data regarding social interaction and natural language analysis are collected.

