On the other hand, the FrailSafe system attempts to depict a subject's frailty status in a more sophisticated and precise way. It consists of various sensors with the ability to record a large amount of data corresponding to several parameters like weight, body fat, blood pressure, pulse waves velocity, heart and respiratory rate, physical strength and activity, postural and movement information, localisation and cognitive performance. Most of the parameters' measurements will take place in real time circumstances in the person's natural environment, in the least invasive way possible. One of the originalities of the project is that the FrailSafe system will be developed and ameliorated during the study's evolution with the help of the preliminary results that will return to the engineers the participant's feedback and experience.

Using this large-scale data collection methodology, it will be possible to make comparisons between the clinical expression of different frailty levels and also between the performance of various measurements and tools to identify and even predict frailty.

Outcomes to be evaluated will be some hard and proxy clinically significant events, the evolution of frailty status of each individual (as measured by structured frailty indices) and the ability of each instrument to measure accurately frailty and its modifications and to predict frailty related outcomes. A secondary outcome (during the phase of parallel Evaluation and Control groups' testing) will be also to evaluate the possible difference in terms of evolution of frailty status between the individuals who received the FrailSafe system feedback and guidance and those who did not. Compliance rates and user satisfaction will be also tested. Shorter periods of monitoring will be compared with longer periods of monitoring to identify cost effective approaches.

By emerging the parameters and instruments the most efficient to detect, quantify and predict frailty, this project aims at constructing new and novel evaluation tools which will serve as frailty biomarkers of high accuracy and predictive value. The translation of these results in clinical practise could contribute to the organisation of strategies to prevent frailty and loss of autonomy both in individual and in population scale.

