Randomization will take place for groups C (Evaluation) and D (Control)(section 2.4) in a later study period (M10-M30). The randomization has proven to be practically difficult for groups A (Start Up) and B (Main), due to the almost coincidence of their recruitment in the beginning of the study and the large number of participants they required. As the dissemination campaign advanced progressively, it turned out to be difficult to have in our availability, since the very initial phase of the clinical study, an even larger pool of participants in order to strictly randomise them. Instead, we included in the first group the first 80 subjects that expressed their interest for participation in each centre, followed by the 40 consequent ones, who were finally allocated to group B. We estimate that since in the present phase of the clinical study the objective is to validate the FrailSafe system and to test its detection sensitivity and not to compare interventions (as will be during the groups C and D parallel evaluations), and since we have no reason to believe that the subjects who were recruited during the first dissemination activities differ significantly from those who were informed about the study in a later stage of the recruitment campaign, the consortium believes that this lack of randomization in the very first phase of the study will not affect results, since comparison between groups will take place later between group C (evaluation) and D (control).

In a later period during the study (M20-M30), recruitment campaigns will start again in order to create the pool of eligible subjects from which participants for group C and D will be randomly selected.

In addition, the participants of the evaluation group C will be further randomized (1:1) into two categories either to receive a tailored set of lifestyle, nutrition and exercise recommendations (predetermined recommendation and "intervention" proposals based on the monitoring performed using the Frailsafe system) or to receive general life style recommendations (standard care). The technical personnel responsible for the extraction and analysis of data will be blind on randomization procedure.

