The participants of group B (40 subjects) started in M10 by the clinical evaluation session. Similarly as in group A, and mainly because of the delay in this first group, the first FrailSafe system installation for group B, along with the blood taking that accompanies it, is not yet completed. The proposed mitigation strategy is described below (section 2.6). In this group the FrailSafe system application will be more intensive, every two or three (only for the first sessions) months, from M12 to M27, for a total of 7 times. The second and third clinical evaluation sessions will take place in M16 and M22 respectively. Finally, a last clinical evaluation session with take place in M35. Telephone follow up assessments will be done every 3 months' time from M26 to M36, but the follow up questionnaire will be administered in person in every FrailSafe home visit also from M12 to M22, during the corresponding appointments. In practice, group B due to its frequent FrailSafe home visits will receive no more than 2 follow up phone calls (M29 and M32). A second blood sampling will take place in M25 only for a subgroup of participants in the clinical center of Patras' University.

The group C will be the group to test the FrailSafe system in its integrity as it will be developed by the interactions and adaptations from the previous groups' experience. Starting in M31 the triplet clinical evaluation, blood sampling and FrailSafe system will be applied. Twenty of the participants in this group will have the FrailSafe system for 5 days (as used by the other groups also), 3 times in total with 2 months' intervals (M31 to M35). On the other hand, five individuals of group C will be asked to carry the FrailSafe system for 60 days in continuation. At the end of the FrailSafe system testing, a satisfaction interview will be conducted to each group C individual. All group C participants will receive a second clinical evaluation in the end of the study (M36) and a follow up questionnaire in M33 for the first arm of group C in M34 by telephone call. A second blood sampling will take place in M35 only for a subgroup of participants in the clinical center of Patras' University.

Finally the group D (control group) will receive no application of the FrailSafe system. A blood sampling will take place in the recruitment (M31), together with a clinical evaluation

session. The latter will be repeated once more at the end (M36). One telephone follow up will take place in M33.

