4.1 All groups

- 1. Quick first verification of inclusion and exclusion criteria
- 2. Randomization to groups (only applicable for group C and D)
- 3. Informed consent and attribution of a unique ID number
- 4. First part of clinical evaluation session: questionnaires to verify inclusion and not inclusion criteria, Fried's criteria of frailty, medical history and cognitive assessment will be administered (tables 4, 5, 6, 9, 13).
- 5. Second verification of the inclusion/exclusion criteria according to the first part of the clinical evaluation's results. If exclusion, replacement of the participant and repetition of steps 1-5 for the next candidate

The steps from this point down and their time programming will differ according to group allocation.

4.2 Group A- Start Up group:

- 1-5. As described above for all groups
- 6. Complete clinical evaluation session (tables 7, 8, 10, 11, 12, 14) (M≥6)
- 7. Data collection regarding social interaction and natural language analysis:
 - Data collection of written text for the first time (table 15), where the participant will either be helped to provide text by dictation or be asked to prepare it him/herself in his/her home and deliver it to us in the next appointment and
 - self-administered questionnaires The Social Media (annex 16) and the Big five (annex 17) questionnaire will be given to participants in order to fill them in themselves and deliver them to us in the next appointment
- 8. First FrailSafe system home visit (M≥6):
 - Blood sampling for telomeres
 - Fill in the evaluation form regarding the participant's housing (table 18)
 - Collect any questionnaires filled in by the participant since the last visit: written texts, social media and big five questionnaires
 - Complete any missing information of the clinical evaluation (i.e. scanning of a forgotten prescription, scanning of an older written text provided by the participant, write down dictated text)
 - Installation of the currently available FrailSafe system and explication of the use, the purposes and the technical issues of the FrailSafe material. Verification of its correct function
 - Provide contact details and instructions in case of any help needed
 - Set the next appointment to retrieve the FrailSafe material (5th day)
- 9. Maintenance of the FrailSafe system at home during 3-5 days

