By following this methodology for groups A and B a considerable amount of continuous data from a large number of participants will be recorded, minimizing the impact of the relatively small number of equipments. It is believed that monitoring these older people, especially of group B, every two months, very little information regarding changes and transition of frailty will be missed. By this time, significant development and many amelioration to the technical aspects of the FrailSafe system is expected to have been achieved.

4.4.1 Group Ci- Standard evaluation group:

- 1-5. As described above for all groups
- 6. Complete clinical evaluation session (tables 5, 7, 8, 10, 11, 12, 14) (M31)
- 7. First FrailSafe system home visit (M31):
 - Blood sampling for telomeres
 - Fill in the evaluation form regarding the participant's housing (table 18)
 - Collect any questionnaires filled in by the participant since the last visit: written texts, social media and big five questionnaires

- Complete any missing information of the clinical evaluation (i.e. scanning of a forgotten prescription, scanning of an older written text provided by the participant, write down dictated text)
- Installation of the currently available FrailSafe system and explication of the use, the purposes and the technical issues of the FrailSafe material. Verification of its correct function
- Provide contact details and instructions in case of any help needed
- Set the next appointment to retrieve the FrailSafe material (5th day)
- 8. Maintenance of the FrailSafe system at home during 5 days
- 9. Short satisfaction interview in the day of FrailSafe system retrieval
- 10. FrailSafe system home visit (M33)
 - Administration of follow up questionnaire (table 17)
 - Installation of the currently available FrailSafe system and reminding of the use, the purposes and the technical issues of the FrailSafe material (Session 3.8). Verification of its correct function
 - Provide contact details and instructions in case of any help needed
 - Set the next appointment to retrieve the FrailSafe material (5th day)
- 11. Maintenance of the FrailSafe system at home during 5 days
- 12. Short satisfaction interview in the day of FrailSafe system retrieval
- 13. Last FrailSafe system home visit (M35). Repetition of steps 12-15.
- 14. [Only for Patras]: Second blood sampling (M35)
- 15. Last clinical evaluation (M36) (tables 5-14)

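### Groups C and D are allocated before a substantial part of their M31 baseline is measured, so unmasked starting values for the C-versus-D comparison can be shifted by knowledge of the arm

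*Protocol*

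**What the plan says.** Section 2.1 names a secondary outcome in these words: "evaluate the possible difference in terms of evolution of frailty status between the individuals who received the FrailSafe system feedback and guidance"; the comparators are people given neither. This is the parallel comparison of group C (evaluation) with group D (control).

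The protocol places allocation at three different points:

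- **Section 3.1:** after the first part of the first visit (subsets 1, 2, 3, 6 and 10) and the eligibility check, but before the remaining subsets: "the randomization and the allocation to groups, the rest of the clinical evaluation takes place (assessment subset 4, 5, 7, 8, 9, 11").
- **Section 4.1:** step 2 is "Randomization to groups (only applicable for group C and D"). Step 3 is "Informed consent and attribution of a unique ID number". The first part of the evaluation is step 4 and the second eligibility check is step 5.
- **Section 2.4:** "Randomization will take place for groups C (Evaluation) and D (Control)(section 2.4) in a later study period (M10-M30"). The same section forms the pool for C and D in M20-M30.

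The baseline is at M31. Section 2.5 says for group C: "Starting in M31 the triplet clinical evaluation, blood sampling and FrailSafe system will be applied". Step 6 in sections 4.4.1, 4.4.2 and 4.5 reads "Complete clinical evaluation session (tables 5, 7, 8, 10, 11, 12, 14) (M31") for both parts of C and for D.

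The only blinding stated is in section 2.4: "The technical personnel responsible for the extraction and analysis of data will be blind on randomization procedure". Elsewhere the arm is visible. Section 2.3 gives C the numbers 121-145 and D the numbers 146-170 at each centre, Table 4 has a group field, and D receives no system.

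**The concern.** A comparison of evolution from M31 to M36 uses the M31 value as its reference. If that value is taken when the participant and the examiner already know the arm, it can carry the effect of that knowledge and is no longer a pure pre-randomisation measurement. A between-arm difference in change can then arise without any effect of FrailSafe.

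The items measured late include ones open to this: self-rated health, quality of life, pain and anxiety (subset 11), ADL/IADL (subset 9), vision and hearing judged by question and impression (subset 7), and timed or effort-dependent tests (subset 5). Section 2.4 itself concedes motivation bias among its volunteers.

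Randomising after consent and after the eligibility check would not cure this, because that is the order in section 3.1. Masking the M36 examiner would not cure it either, because the M31 value is what is exposed.

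**Working it through.** The protocol gives no power or error figure for C versus D, so there is none to reproduce. The head count is consistent: 3 × 25 = 75 per arm, and 3 × (80 + 40 + 25 + 25) = 510 in all.

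**1. Subsets measured after allocation.** Under section 3.1: 4, 5, 7, 8, 9 and 11, that is 6 of 11. Under section 4.1, or the dates in 2.4: all 11. No section puts allocation after a complete baseline.

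**2. Clinical Frailty Index entries (Table 22).** By domain: 6 + 2 + 7 + 5 + 4 + 3 + 8 + 3 + 5 + 3 = 46. Those in the late subsets under section 3.1:

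- orthostatic hypotension, vision, hearing: 3
- balance, Timed Get Up and Go, 4 m gait, chair rise, qualitative mobility: 5
- low BMI, high BMI, waist, lean mass, MNA: 5
- anxiety, in the psychological domain: 1
- wellness domain: 5

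Total 19; 19/46 = 41%. The other 27 are 22 entries collected in the first part, 3 housing entries from the home visit (which D never has) and 2 natural-language entries with no clear place in the order.

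**3. Allowance for Fried's criteria.** Section 3.1 puts these before allocation. Table 9 needs the walking test and height for slowness, and BMI (hence height and weight) for grip. These parts of subsets 4 and 5 must then be available early. Removing 4 m gait, low BMI and high BMI leaves 19 − 3 = 16; 16/46 = 35%.

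**4. Outcomes (sections 5.2.1 and 5.2.2).** Of the five proxy outcomes, MoCA/MMSE and GDS come before allocation under 3.1. Gait speed and weight come after it by the listing, but probably before it by step 3. Health self-assessment is clearly after. So are the ADL/IADL values from which a one-point decline, a hard outcome, is counted.

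**5. Gap under section 2.4.** With the pool formed in M20-M30 and baseline at M31, the gap is 31 − 30 = 1 to 31 − 20 = 11 months.

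**6. Illustration of the mechanism.** The assumptions, none from the protocol, are 75 per arm, two-sided 5%, no true effect, baseline-final correlation r, an arm-dependent shift of b SD at M31, and a fraction p of it still present at M36.

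- Change score: bias of size (1 − p)b; SE = √(2(1 − r)) × √(2/75), which is 0.163 at r = 0.5 and 0.126 at r = 0.7.
- Baseline-adjusted: bias of size |p − r|b; SE = √(1 − r²) × √(2/75), which is 0.141 at r = 0.5.
- Error rate = Φ(z − 1.96) + Φ(−z − 1.96), with z = bias/SE.

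| Analysis | r | p | b = 0.1 | b = 0.2 | b = 0.3 |
|---|---|---|---|---|---|
| Change | 0.5 | 0 | 9% | 23% | 45% |
| Change | 0.7 | 0 | 12% | 35% | 66% |
| Change | 0.5 | 0.5 | 6% | 9% | 15% |
| Change | any | 1 | 5% | 5% | 5% |
| Adjusted | 0.5 | 0 | 6% | 11% | 19% |
| Adjusted | 0.7 | 0 | 9% | 23% | 44% |

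Adjustment removes the bias only if p happens to equal r.

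**7. Direction.** If C looks better than D at M31 (b = 0.2, r = 0.5, p = 0), z = 0.2/0.163 = 1.22. The chance of a significant change favouring FrailSafe is Φ(−1.96 − 1.22) ≈ 0.07%, against a nominal 2.5%.

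**The case against.** The strongest reply is that the exposure is partial and its effect unknown. Several parts of that stand.

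- A reader might infer that most of the baseline follows allocation. By subsets under section 3.1 that is a bare majority (6 of 11); by index entries it is 35% to 41%. Fried's criteria, comorbidities, medication, cognition and GDS precede allocation there. Some late entries, such as waist, lean mass and blood pressure, leave little room for expectation.
- A reader might count three of five proxy outcomes as exposed. The needs of Fried's criteria make that unsafe for gait speed and weight.
- A reader might take M10 literally and report a gap of up to 21 months. Nobody can be drawn from a pool that starts forming in M20, so about 11 months is the limit. Loss between allocation and baseline is a worry only on the 2.4 dates; in 3.1 both fall within the first evaluation.
- A reader might take 23% or 45% as the trial's error rate. Those figures assume the full shift at M31, none at M36, and a shift acting on the whole outcome.
- A reader might assume that the bias favours FrailSafe. Disappointed controls or motivated device users would make C look better at M31, which works against it. Examiner expectation could go either way.
- Group C is itself randomised 1:1 to tailored or general recommendations, so 75 versus 75 may not be the contrast meant in section 2.1. No test for it is specified in the protocol, and the comparison is secondary. Falls, fractures, non-programmed hospitalisation, institutionalisation and death need no M31 score.

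These points limit the size of the problem but leave the sequence as it is. Every statement of timing puts allocation before some or all of the baseline, and none masks the participant or the clinical examiner at M31.

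**Conclusion.** The point holds as an avoidable exposure to bias in a secondary comparison. Followed as written, the protocol measures at least 16 to 19 of 46 index entries, the self-rated health proxy and the ADL/IADL reference values after allocation and without masking. Under sections 4.1 and 2.4 this extends to the whole M31 clinical baseline. The three sections also contradict one another on when allocation happens, and 4.1 lists it before consent.

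The amount of bias cannot be derived from the protocol. It depends on the shift, on how much of it persists to M36 and on the correlation, and the protocol gives none of these. The error rates show only that a modest shift can matter at 75 per arm and that baseline adjustment is no general remedy. The documents support neither a specific error rate nor a claim that results would be tilted towards FrailSafe.

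This should be changed before groups C and D start. It does not touch the main objective of detecting and predicting frailty.

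**What to change.** Reconcile sections 2.4, 3.1, 4.1, 4.4.1, 4.4.2 and 4.5 to one order for groups C and D:

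1. Use M20-M30 only to recruit the pool, and remove M10-M30 as the allocation window.
2. At M31, obtain consent, confirm eligibility and complete all baseline clinical subsets, including the present step 6.
3. Only then make or disclose the C/D assignment and the tailored/general assignment within C, whose timing relative to baseline is not stated now.
4. Use a neutral number until then. Assign the group-specific ID (section 2.3) and fill in the Table 4 group field after baseline. Table 4 belongs to subset 1, which section 3.1 places before randomisation, so the form as drawn up asks for the arm too early.

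The cost is protocol wording, a re-ordering of steps in the same visit and a temporary number on the form. No visit, test or participant is added and the group sizes stay the same. No clinical baseline subset would then be measured with knowledge of the arm.
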